13.7 Publications and Clinical Study Report

13.7.1 Publication of Study Results

Vertex is committed to reporting the design and results of all clinical studies in a complete, accurate, balanced, transparent, and timely manner, consistent with Good Publication Practices (GPP3).¹⁹

Publication Planning: Vertex staff along with the lead principal investigators (PIs), the steering committee (SC), and/or the publication committee (PC) will work together to develop a publication plan.

Authorship: Authorship of publications will be determined based on the Recommendations for Conduct, Reporting, Editing, and Publication of Scholarly Work in Medical Journals, which states that authorship should be based on the following 4 criteria²⁰:

1. Substantial contributions to conception and design, acquisition of data, or analysis and interpretation of data;
2. Drafting of the article or revising it critically for important intellectual content;
3. Final approval of the version to be published; and
4. Agreement to be accountable for all aspects of the work in ensuring that questions related to the accuracy or integrity of any part of the work are appropriately investigated and resolved.

All authors must meet conditions 1, 2, 3, and 4. All persons designated as authors should qualify for authorship, and all those who qualify should be listed. Contributions such as medical writing, enrollment of subjects, acquisition of funding, collection of data, or general supervision of the research group, alone, do not justify authorship.

Contributors: Contributors who meet fewer than all 4 of International Committee of Medical Journal Editors (ICMJE) criteria for authorship will not be listed as authors, but their contribution will be acknowledged and specified either as a group (e.g., “study investigators”) or individually (e.g., “served as scientific advisor”).

Publication Review: As required by a separate clinical study agreement, Vertex must have the opportunity to review all publications, including any manuscripts, abstracts, oral/slide presentations, and book chapters regarding this study before submission to congresses or journals for consideration.

13.7.2 Clinical Study Report

A CSR, written in accordance with the current ICH E3 Guideline, will be submitted in accordance with local regulations.

APPENDIX A Eligible MF *CFTR* Mutations

“MF” mutations are a subset of minimal function mutations that are non-responsive to IVA and TEZ/IVA. A mutation is considered an MF mutation if it meets at least 1 of the following 2 criteria:

- (1) No biological plausibility of translated protein (genetic sequence predicts the complete absence of CFTR protein), or
- (2) in vitro testing that supports lack of responsiveness to IVA and TEZ/IVA.

Inclusion of MF Mutations Based on In Vitro Testing

Mutations that were considered to be MF mutations based on in vitro testing met the following criteria in in vitro experiments:

- baseline chloride transport that was <10% of wildtype CFTR
- an increase in chloride transport of <10% over baseline following the addition of IVA and TEZ/IVA in the assay

Eligible MF Mutations

The mutations below are detectable by an FDA-cleared genotyping assay or other method (e.g., sequencing).

This list does not include every eligible mutation, and investigators should contact the medical monitor regarding other mutations that may also meet study eligibility criteria.

Non-exhaustive List of Minimal Function *CFTR* Mutations Eligible for VX19-445-117

Q2X	L218X	Q525X	R792X	E1104X
S4X	Q220X	G542X	E822X	W1145X
W19X	Y275X	G550X	W882X	R1158X
G27X	C276X	Q552X	W846X	R1162X
Q39X	Q290X	R553X	Y849X	S1196X
W57X	G330X	E585X	R851X	W1204X
E60X	W401X	G673X	Q890X	L1254X
R75X	Q414X	Q685X	S912X	S1255X
L88X	S434X	R709X	Y913X	W1282X
E92X	S466X	K710X	Q1042X	Q1313X
Q98X	S489X	Q715X	W1089X	Q1330X
Y122X	Q493X	L732X	Y1092X	E1371X
E193X	W496X	R764X	W1098X	Q1382X
W216X	C524X	R785X	R1102X	Q1411X
185+1G>T	711+5G>A	1717-8G>A	2622+1G>A	3121-1G>A
296+1G>A	712-1G>T	1717-1G>A	2790-1G>C	3500-2A>G
296+1G>T	1248+1G>A	1811+1G>C	3040G>C (G970R)	3600+2insT
405+1G>A	1249-1G>A	1811+1.6kbA>G		3850-1G>A
405+3A>C	1341+1G>A	1811+1643G>T	3120G>A	4005+1G>A
406-1G>A	1525-2A>G	1812-1G>A	3120+1G>A	4374+1G>T
621+1G>T	1525-1G>A	1898+1G>A	3121-2A>G	
711+1G>T		1898+1G>C		
182delT	1119delA	1782delA	2732insA	3791delC
306insA	1138insG	1824delA	2869insG	3821delT
365-366insT	1154insTC	1833delT	2896insAG	3876delA
394delTT	1161delC	2043delG	2942insT	3878delG
442delA	1213delT	2143delT	2957delT	3905insT
444delA	1259insA	2183AA>G ^a	3007delG	4016insT
457TAT>G	1288insTA	2184delA	3028delA	4021dupT
541delC	1343delG	2184insA	3171delC	4022insT
574delA	1471delA	2307insA	3171insC	4040delA
663delT	1497delGG	2347delG	3271delGG	4279insA
849delG	1548delG	2585delT	3349insT	4326delTC
935delA	1609del CA	2594delGT	3659delC	
1078delT	1677delTA	2711delT	3737delA	

Non-exhaustive List of Minimal Function *CFTR* Mutations Eligible for VX19-445-117

CFTRdele1	CFTRdele16-17b	991del5
CFTRdele2	CFTRdele17a,17b	1461ins4
CFTRdele2,3	CFTRdele17a-18	1924del7
CFTRdele2-4	CFTRdele19	2055del9>A
CFTRdele3-10,14b-16	CFTRdele19-21	2105-2117del13insAGAAA
CFTRdele4-7	CFTRdele21	2372del8
CFTRdele4-11	CFTRdele22-24	2721del11
CFTR50kdel	CFTRdele22,23	2991del32
CFTRdup6b-10	124del23bp	3121-977_3499+248del2515
CFTRdele11	306delTAGA	3667ins4
CFTRdele13,14a	602del14	4010del4
CFTRdele14b-17b	852del22	4209TGTT>AA

A46D	V520F	Y569D	N1303K
G85E	A559T	L1065P	
R347P	R560T	R1066C	
L467P	R560S	L1077P	
I507del	A561E	M1101K	

CFTR: cystic fibrosis transmembrane conductance regulator gene

Source: CFTR2.org. Clinical and functional translation of CFTR. The Clinical and Functional Translation of CFTR (CFTR2), US Cystic Fibrosis Foundation, Johns Hopkins University, the Hospital for Sick Children. Available at: <http://www.cfr2.org>. Accessed 15 February 2016.

[figure not shown]
^a Also known as 2183delAA>G.

## **2                    MODIFICATIONS**

### **2.1                Modifications to the Approved Clinical Study Protocol**

Not Applicable.

### **2.2                Modifications to the Approved Statistical Analysis Plan**

Not Applicable. This is the 1st version of Statistical Analysis Plan.

### **3 INTRODUCTION**

Study VX19-445-117 is a Phase 3b open-label study evaluating the effect of elexacaftor (ELX, VX-445) in triple combination (TC) with tezacaftor (TEZ) and ivacaftor (IVA) on glucose tolerance in cystic fibrosis (CF) subjects who are 12 years of age and older, heterozygous for *F508del* and a minimal function mutation (F/MF), and with abnormal glucose metabolism.

This statistical analysis plan (SAP) is based on the most recent approved clinical study protocol (CSP), the most recent approved electronic case report form (eCRF), and the most recent approved eCRF completion guidelines.

This SAP (Methods) version 1.0 documents the planned statistical analyses of efficacy and safety endpoints for final analysis. It also documents analyses for additional efficacy and safety variables not specified in the protocol, which will provide supportive information for the scientific understanding of the drug entity.

The Vertex Biometrics Department will perform the statistical analysis of efficacy and safety data. SAS (Version 9.4 or higher) will be used to generate all statistical outputs (tables, figures, listings, and datasets). The SAP (version 1.0) will be finalized and approved prior to the clinical database lock for the study. Any revisions to the approved SAP will be documented and approved in an amendment to the SAP.

### **4 STUDY OBJECTIVES**

#### **4.1 Primary Objective**

To evaluate the effect of ELX/TEZ/IVA on glucose tolerance in CF subjects with impaired glucose tolerance (IGT) or CF-related diabetes (CFRD)

#### **4.2 Secondary Objectives**

To evaluate the safety and tolerability of ELX/TEZ/IVA

### **5 STUDY ENDPOINTS**

#### **5.1 Efficacy and Pharmacodynamic Endpoints**

##### **5.1.1 Primary Endpoint**

Change from baseline in 2-hour blood glucose levels following an oral glucose tolerance test (OGTT) to the average of Week 36 and Week 48

##### **5.1.2 Secondary Endpoint**

- Proportion of subjects with improvement in dysglycemia categorization (CFRD, IGT, normal glucose tolerance [NGT]) at Week 48
- Safety and tolerability of ELX/TEZ/IVA based on adverse events (AEs), clinical laboratory values, ECGs, vital signs, and pulse oximetry

##### **5.1.3 Other Endpoints**

- Change from baseline in sweat chloride (SwCl) through Week 48
- Absolute change in body mass index (BMI) from baseline at Week 48

- Absolute change in body weight from baseline at Week 48
- Change from baseline in hemoglobin A1c (HbA1c) and fructosamine at Week 48
- Change from baseline in insulin use (dose) at Week 48 in subjects using insulin
- Change from baseline in post-OGTT diabetes-related biomarkers (including insulin, C-peptide, glucagon, calculated indices of insulin secretion [insulinogenic index], and insulin resistance [HOMA-IR]) at Week 48
- Change from baseline in biomarkers of inflammation (including C-reactive protein [CRP]) at Week 48
- Change from baseline in biomarkers of pancreatic function (including fecal elastase-1 [FE-1] and serum immunoreactive trypsinogen [IRT]) at Week 48
- Change from baseline in post-OGTT incretin levels (including glucagon-like peptide 1 [GLP-1] and glucose-dependent insulinotropic polypeptide [GIP]) at Week 48
- Change from baseline in percent of time spent in target blood glucose range of  $\geq 70$  to  $< 140$  mg/dL ( $\geq 3.89$  to  $< 7.77$  mmol/L) as measured by 7-day continuous glucose monitoring (CGM) in subjects with CFRD at Week 48
- Change from baseline in selected CGM parameters (including but not limited to percent of time spent between  $\geq 140$  and  $< 200$  mg/dL [ $\geq 7.77$  and  $< 11.10$  mmol/L], percent of time spent  $\geq 200$  mg/dL [ $\geq 11.10$  mmol/L], and mean amplitude of glycemic excursion\* [MAGE]) in subjects with CFRD at Week 48

[figure not shown]
\*Note: definition corrected for MAGE (originally defined as maximum amplitude of glucose excursions in the study protocol).

## **6 STUDY DESIGN**

### **6.1 Overall Design**

This is a Phase 3b, open-label study in CF subjects 12 years of age and older with F/MF genotypes and abnormal glucose tolerance as shown in [Figure 7-1](#).

Approximately 60 subjects (F/MF genotypes) will be enrolled, of whom approximately 30 subjects will have IGT, and 30 subjects will have CFRD. During the Treatment Period, subjects will be administered ELX/TEZ/IVA for approximately 48 weeks. All subjects will receive ELX 200 mg once daily (qd)/TEZ 100 mg qd/ IVA 150 mg every 12 hours (q12h).

## 6.2 Sample Size and Power

The primary efficacy endpoint is change from baseline in 2-hour blood glucose levels following an OGTT to the average of Week 36 and Week 48. The primary null hypothesis to be tested is that the mean change from baseline in 2-hour blood glucose levels following OGTT to the average of Week 36 and Week 48 is equal to zero.

Assuming a within group standard deviation (SD) of 45 mg/dL and a 10% dropout rate at Week 48, a sample size of 60 subjects will have more than 95% power to detect a mean decrease from baseline of -30 mg/dL in 2-hour blood glucose levels post-OGTT to the average of Week 36 and Week 48, based on a 2-sided, 1-sample t-test at a significance level of 0.05.

All power calculations were based on EAST software Version 6.4.

## 6.3 Randomization

Not applicable.

## 6.4 Blinding and Unblinding

This is an open-label study. Refer to Section 10.7 of the CSP for details.

## 7 ANALYSIS SETS

The following analysis sets are defined: All Subjects Set, Full Analysis Set (FAS), Safety Set

## 7.1 All Subjects Set

The **All Subjects Set** will include all subjects who were enrolled (defined as subjects having data in the clinical database for this study). This analysis set will be used for all individual subject data listings and disposition summary tables, unless otherwise specified.

## 7.2 Full Analysis Set

The **Full Analysis Set** (FAS) will include all enrolled subjects who carry the intended CFTR allele mutation and have received at least 1 dose of study drug. The FAS will be used to summarize subject demographics and baseline characteristics, and for analyses of all efficacy endpoints, unless otherwise specified.

## 7.3 Safety Set

The **Safety Set** will include all subjects who have received at least 1 dose of study drug. The Safety Set is to be used for all safety analyses.

# 8 STATISTICAL ANALYSIS

## 8.1 General Considerations

**Continuous variables** will be summarized using the following descriptive summary statistics: the number of subjects (n), mean, SD, median, minimum value (min), and maximum value (max).

**Categorical variables** will be summarized using counts and percentages.

**Baseline value**, unless otherwise specified, will be defined as the most recent non-missing measurement (scheduled or unscheduled) collected before the first dose of study drug in the Treatment Period. The baseline 2-hour post-OGTT blood glucose level will be the average of pre-dose measurements at Screening and Day 1 visits (if both measurements are not available, use one measurement).

**Absolute change** from baseline will be calculated as post-baseline value – baseline value.

**Relative change** from baseline will be calculated as (post-baseline value – baseline value)/baseline value.

**Treatment-emergent (TE) Period** will include the time from the first dose of study drug to 28 days after the last dose of study drug or to the completion of study participation, whichever occurs first. Refer to Section 9.1.6 of the CSP for the definition of completion of study participation.

**Unscheduled visits:** Unscheduled visit measurements will be included in analysis as follows:

- 1) In scheduled visit windows per specified visit windowing rules
- 2) In the derivation of baseline and last on-treatment measurements
- 3) In the derivation of maximum and minimum values during TE period, and maximum and minimum change from baseline values during TE period for safety analyses
- 4) In individual subject data listings as appropriate

**Visit windowing rules:** The analysis visit windows for protocol-defined visits are provided in [Appendix A](#).

**Incomplete/missing data** will not be imputed, unless specified otherwise.

**Outliers:** No formal statistical analyses will be performed to detect or remedy the presence of statistical outliers, unless specified otherwise.

## **8.2 Background Characteristics**

### **8.2.1 Subject Disposition**

The number of subjects in the following categories will be summarized based on the All Subjects Set:

- All Subject Set
- FAS
- Safety Set

The number and percentage (based on FAS) of subjects in each of the following disposition categories will be summarized:

- Completed study drug treatment
- Prematurely discontinued treatment (i.e., discontinued all study drugs) and the reason for discontinuation
- Completed study
- Prematurely discontinued the study and the reason for discontinuation
- Rollover to the open-label study

A listing will be provided for subjects who discontinued treatment or who discontinued study with reasons for discontinuation.

### **8.2.2 Demographics and Baseline Characteristics**

Demographics and baseline characteristics will be summarized based on the FAS.

Demographic data will include the following:

- Age at baseline (in years)
- Sex (female and male)
- Ethnicity (Hispanic or Latino, not Hispanic or Latino, and not collected per local regulations)
- Race (White, Black or African American, Asian, American Indian or Alaska Native, Native Hawaiian or Other Pacific Islander, Other, and not collected per local regulations)
- Country

Baseline characteristics will include the following:

- Weight (kg)
- Height (cm)
- BMI (kg/m^2)

Disease characteristics will include the following:

- ppFEV1 at baseline (<30, ≥30 to <40, ≥40 to <70, ≥70 to ≤90, and >90)
- ppFEV1 at baseline (continuous)
- Sweat chloride at baseline (continuous)
- 2-hour post-OGTT blood glucose levels at baseline (continuous)
- Dysglycemia categorization at screening (IGT, CFRD)
- Insulin use at baseline (Yes, No)
- Prior use of dornase alfa (Yes, No)
- Prior use of azithromycin (Yes, No)
- Prior use of inhaled antibiotic (Yes, No)
- Prior use of bronchodilator (Yes, No)
- Prior use of inhaled bronchodilator (Yes, No)
- Prior use of inhaled hypertonic saline (Yes, No)
- Prior use of inhaled corticosteroids (Yes, No)

In addition, data listings will also be provided for:

- Informed consent;
- Inclusion/Exclusion criteria violation for subjects with any such violations.

The predicted FEV1 will be calculated using the Global Lung Function Initiative (GLI); details are provided in [Appendix B](#).

### **8.2.3 Medical History**

Medical history will be coded by using the Medical Dictionary for Regulatory Activities (MedDRA). Medical history will be summarized descriptively by System Organ Class (SOC) and Preferred Term (PT) for the FAS. The corresponding data listing will also be provided.

### **8.2.4 Prior and Concomitant Medications**

Medications will be coded using the World Health Organization Drug Dictionary (WHO-DD) and categorized as follows:

**Prior medication:** any medication that was administered during the 56 days before the first dose of study drug.

**Concomitant medication:** medication continued or newly received during the TE period

**Post-treatment medication:** medication continued or newly received after the TE period

A given medication may be classified as prior, concomitant, or post treatment; both prior and concomitant; both concomitant and post treatment; or prior, concomitant, and post treatment.

If a medication has a missing or partially missing start/end date or time and if it cannot be determined whether it was taken before the first dose of study drug, concomitantly during the TE

Period, or after the TE Period, it will be considered in all 3 categories of prior, concomitant, and post treatment medication. Details for imputing missing or partial start and/or stop dates of medication are described in [Appendix C](#).

Prior medications and concomitant medications will be summarized descriptively using frequency tables by: 1) preferred name (PN); and 2) anatomic class (ATC) level 1, ATC level 2, and PN for FAS. All medications will be listed for each subject.

The number of subjects who used hormonal therapy concomitantly during the Treatment Period will be summarized based on the Safety Set.

### **8.2.5 Study Drug Exposure**

Study drug exposure will be summarized based on the Safety Set.

Duration of study drug exposure (in weeks) will be calculated as: (last dose date of study drug – first dose date of study drug + 1)/7, regardless of study drug interruption.

Study drug exposure (in weeks) will be summarized descriptively by the number of subjects (n), mean, SD, median, min, and max. It will also be summarized by intervals, using counts and percentages.

### **8.2.6 Study Drug Compliance**

Study drug compliance will be summarized based on the FAS.

Study drug compliance will be calculated as:  $100 \times [1 - (\text{total number of days of study drug interruption}) / (\text{duration of study drug exposure in days})]$ . A study drug interruption on a given day is defined as an interruption of any study drugs on that day. A study drug interruption that continues through the end of the study participation (i.e., subject does not resume study drug before the end of the study participation) will not be included in the compliance calculation.

Study drug compliance will be summarized descriptively by the number of subjects (n), mean, SD, median, min, and max. It will also be summarized in categories: <80% and ≥80% using frequency tables.

### **8.2.7 Important Protocol Deviations**

An important protocol deviation (IPD) is a deviation that may significantly affect the completeness, accuracy, or reliability of the study data or that may significantly affect a subject's rights, safety, or well-being. A protocol deviation review team will categorize IPDs according to the Protocol Deviation Plan during the study.

IPDs will be only provided in an individual subject data listing.

## **8.3 Efficacy Analysis**

Unless otherwise defined, all efficacy analyses described in this section will be based on the FAS.

### **8.3.1 Analysis of Primary Efficacy Variable**

#### **8.3.1.1 Definition of Variable**

The primary efficacy endpoint is change from baseline in 2-hour glucose levels following an OGTT to the average of Week 36 and Week 48.

2-hour blood glucose levels following an OGTT: OGTT will be performed to assess 2-hour glucose levels. Depending on a subject's weight, 1.75 g/kg of body weight or 75 g maximum of oral glucose solution will be administered in the morning after at least 8 hours of fasting. Blood samples will be obtained at 0, 30 ( $\pm 5$ ), 60 ( $\pm 5$ ), 90 ( $\pm 5$ ), and 120 ( $\pm 5$ ) minutes after the start of ingestion of glucose solution. OGTT results are considered valid only when the subject was fasting for at least 8 hours. Any non-fasting OGTT results will be disregarded and data for that assessment will be considered missing.

### 8.3.1.2 Primary Analysis

The primary analysis will be performed using a mixed-effects model for repeated measures (MMRM) with the change from baseline in 2-hour post-OGTT blood glucose levels at each post-baseline visit as the dependent variable. The model will include visit as a fixed effect, with continuous baseline 2-hour post-OGTT blood glucose level as covariate. The model will be estimated using restricted maximum likelihood. Denominator degrees of freedom for the  $F$ -test for fixed effects will be estimated using the Kenward-Roger approximation. An unstructured covariance structure will be used to model the within-subject errors. If the model estimation does not converge, a compound symmetry covariance structure will be used instead. Conditional on the observed data and covariates, missing data will be assumed to be missing at random and therefore will be handled by MMRM model.

The primary result obtained from the model will be the estimated change from baseline to the average of Week 36 and Week 48. Data obtained from Week 24, Week 36, and Week 48 visits will be included in the model. The least square (LS) mean estimate along with the corresponding 2-sided 95% confidence interval (CI) and  $P$  value will be provided. The LS mean change from baseline at each post-baseline visit with 95% CI, obtained from the model, will also be provided. Furthermore, the LS mean change from baseline (with SE) at each post-baseline visit, obtained from the model, will be plotted.

In addition, the post-baseline raw values and the change from baseline at each post-baseline visit up to Week 48 will be summarized descriptively (n, mean, SD, median, minimum, and maximum).

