8.1 Inclusion Criteria

1. Subject (or his or her legally appointed and authorized representative) will sign and date an informed consent form (ICF), and, when appropriate, an assent form.
2. Willing and able to comply with scheduled visits, treatment plan, study restrictions, laboratory tests, contraceptive guidelines, and other study procedures.
3. Subjects (male and female) 12 years of age or older on the date of informed consent.
4. Subjects heterozygous for *F508del* and an MF mutation (F/MF genotypes, see [Appendix A](#) for definition and non-exhaustive list of eligible MF mutations).
 - a. Genotype should be confirmed at the Screening Visit.
 - b. If the screening *CFTR* genotype result is not received before the first dose of study drug, a previous *CFTR* genotype laboratory report may be used to establish eligibility.
 - c. Subjects who have been enrolled and whose screening genotype does not confirm study eligibility must be discontinued from the study (Section 9.9).
5. Forced expiratory volume in 1 second (FEV₁) value $\geq 30\%$ of predicted mean for age, sex, and height (equations of the Global Lung Function Initiative [GLI])⁹ at the Screening Visit (spirometry measurements must meet American Thoracic Society/European Respiratory Society criteria¹⁰ for acceptability and repeatability) and stable CF disease as judged by the investigator.
6. Willing to remain on a stable CF treatment regimen (other than *CFTR* modulators) through completion of study participation.
7. Abnormal glucose tolerance as determined by an OGTT, classified as either IGT (defined as 2-hour post-OGTT blood glucose level ≥ 140 to < 200 mg/dL [≥ 7.77 to < 11.10 mmol/L]) or CFRD (defined as either fasting hyperglycemia [blood glucose level ≥ 126 mg/dL (≥ 7.00 mmol/L) after an 8-hour fast] or 2-hour post-OGTT blood glucose level ≥ 200 mg/dL [≥ 11.10 mmol/L]).

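### The primary LS mean is planned without a reference baseline; if it is taken at the sample mean baseline, its SE ignores the sampling variation of that mean, so the reported CI is somewhat too narrow as an interval for the population mean change

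*SAP*

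**What the plan says.** **Hypothesis.** SAP 6.2 (and Protocol 12.1) puts the null on the mean change itself: "The primary null hypothesis to be tested is that the mean change from baseline in 2-hour blood glucose levels following OGTT", to the average of Weeks 36 and 48, is zero. There is one arm, and Protocol 9.3.1 relies on within-group comparison.

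**Sizing.** A two-sided one-sample t-test with SD 45 mg/dL, 60 subjects, 10% dropout and an effect of -30 mg/dL (SAP 6.2).

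**Primary analysis.** SAP 8.3.1.2 fits change at Weeks 24, 36 and 48 by REML with unstructured covariance and Kenward-Roger degrees of freedom: "The model will include visit as a fixed effect, with continuous baseline 2-hour post-OGTT blood glucose level as covariate". The LS mean for the Week 36/48 average is reported with a 95% CI and P value. The baseline value at which it is evaluated is not stated. On convergence failure: "If the model estimation does not converge, a compound symmetry covariance structure will be used instead".

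**Baseline.** "The baseline 2-hour post-OGTT blood glucose level will be the average of pre-dose measurements at Screening and Day 1 visits" (SAP 8.1).

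**Raw data.** According to SAP 8.3.1.2, "the post-baseline raw values and the change from baseline at each post-baseline visit up to Week 48 will be summarized descriptively". This gives no CI or test for the Week 36/48 average.

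**Mix.** About 60 subjects, "of whom approximately 30 subjects will have IGT, and 30 subjects will have CFRD" (SAP 6.1).

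**The concern.** In a randomised comparison, error in the mean baseline largely cancels from the difference between arms. Here there is no second arm. With complete data, the LS mean at the sample mean baseline is simply the raw mean change, and its sampling variance includes the variation that comes through baseline. The model's SE treats the mean baseline as a known constant and leaves that part out. REML and Kenward-Roger also condition on the covariate, so they do not put it back.

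Some negative correlation between change and baseline is expected, because error in the baseline OGTTs enters baseline with a plus sign and change with a minus sign. At stake are the precision claimed for the trial's main estimate, and the error rate if the true mean change is near zero.

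**Working it through.** **1. The plan's own figure.** One-sample t-test, n = 60 × 0.9 = 54, SD 45, effect 30. Noncentrality is (30/45) × √54 = 4.90, and power is 99.8%. The stated power above 95% is reproduced. The SE here is 45/√54 = 6.12 mg/dL, which includes the baseline part.

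**2. Size of the missing part (complete data, n = 54).** Let ρ be the correlation of change with baseline. This is an assumption; the documents give no value.

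- Model variance: SD²(1 - ρ²)/n. Missing part: slope² × Var(baseline)/n = SD²ρ²/n.
- ρ = -0.20: model SE √(37.5 × 0.96) = 6.00; missing variance 1.50.
- ρ = -0.30: model SE √(37.5 × 0.91) = 5.84; missing variance 3.38.
- ρ = -0.55: model SE √(37.5 × 0.6975) = 5.11; missing variance 11.34.

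In each case the two parts sum to 37.5 = 6.12².

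**3. Error rate, closed form.** Type I error = 2[1 - Φ(1.96 × √{(1 - ρ²)/(1 - ρ² + fρ²)})]. Here f is the share of the term that is really missing: f = 1 if the IGT/CFRD mix is left to chance, and about 0.5 if it is held exactly at 1:1. The categories are defined largely by 2-hour glucose (Protocol 8.1), so fixing the mix fixes part of the baseline variance; the within-category share was 0.52 in the simulations. For ρ = -0.2, -0.3, -0.4 and -0.5 the results are 5.5%, 6.2%, 7.2% and 9.0% with f = 1, and 5.2%, 5.6%, 6.1% and 7.0% with f = 0.5.

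**4. Simulation of the planned MMRM.** Inputs from the SAP: 60 enrolled, 10% dropout, SD of change 45, three visits, unstructured covariance, REML, Kenward-Roger. Assumed inputs: true 2-hour glucose with mean 190 and SD 50; within-person OGTT SD 35; entry if the screening value is at least 140; IGT/CFRD cut at 200, ignoring the fasting criterion; slope of response on true glucose 0, -0.15, -0.30 or -0.45; dropout completely at random. There were 7,000 trials per cell, with a Monte Carlo SE of 0.2 to 0.4 point.

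| Slope | ρ | Model v true SE, chance mix | Type I, chance | Model v true SE, exact 1:1 | Type I, exact |
|---|---|---|---|---|---|
| 0 | -0.20 | 5.88 v 6.02 | 5.5% | 5.89 v 5.94 | 4.9% |
| -0.15 | -0.32 | 5.71 v 6.04 | 6.2% | 5.69 v 5.86 | 6.0% |
| -0.30 | -0.43 | 5.42 v 5.96 | 7.4% | 5.43 v 5.69 | 6.2% |
| -0.45 | -0.55 | 5.00 v 5.91 | 9.8% | 5.01 v 5.51 | 7.5% |

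A simpler check with one outcome per subject (n = 54) gave 5.2%, 6.4%, 7.4% and 10.4% (chance) and 5.4%, 5.4%, 6.8% and 7.9% (exact).

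**5. CI half-width, chance mix.** The planned model gives about 11.7, 11.4, 10.8 and 10.0 mg/dL in the four rows; with the term added it is about 12.0.

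**6. With the term added.** Type I error is 4.8%, 4.9%, 4.9% and 5.0% (chance) and 4.3%, 4.6%, 3.9% and 2.9% (exact).

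**7. At a true change of -30 mg/dL.** The decision differs between the planned and corrected analyses in 0% to 0.2% of trials (2,000 per cell). Power after correction is 99.6% to 100%.

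**The case against.** **The SE is valid given the observed baselines.** This is true, and the null does not say whether baselines are fixed or random. But it is worded as the mean change, not the mean at a given baseline, and the sizing uses a variance that counts baseline variation. The SAP does not declare a conditional target.

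**The documents support only a small effect.** This largely stands. The one mechanism they name is OGTT variability (Protocol 9.3.1). In the input model, measurement error alone gives ρ of -0.10, -0.20 and -0.30 for a within-person SD of 25, 35 and 44, and about 44 is near the largest value compatible with an SD of change of 45. Larger correlations need a response slope that no passage supplies.

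**Near a 1:1 mix the repair overcorrects.** This also stands: at ρ = -0.55, 7.5% becomes 2.9%. That is the safer direction, and the mix is only approximate.

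**Stronger readings that a reader might infer.**

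- *Error rates up to 13% in this trial.* That figure comes from a scenario at ρ about -0.65 (chance mix) with a -0.45 slope and different glucose inputs. It is an illustration, not an estimate.
- *The CI is too narrow whenever change correlates with baseline.* The shortfall holds on average. In one sample the model SE is smaller only if r² > 1/(n - 1), and one simulated cell with a non-zero correlation gave 4.9%.
- *The benchmark is the t-test half-width, 2.006 × 6.12 = 12.3 mg/dL.* The MMRM also uses incomplete subjects, so its correct width is about 12.0 with a chance mix. With an exact mix it is about 11.9 at ρ = -0.20, falling to 10.7 at -0.65.
- *The type I error is the risk of calling an inactive drug active.* It is not. Entry depends on the screening OGTT, which is half of baseline, so in the first four scenarios an inactive drug would show a mean change of about -3.0 to -3.6 mg/dL. That is a separate matter; the simulations set the mean change to zero.
- *Baseline adjustment is itself a mistake.* Protocol 12.3.3.1 allows covariates, and the adjustment is useful for missing data.

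**Conclusion.** The point holds in a limited form. The SAP should state where the LS mean is evaluated. If that is the sample mean baseline, the SE is on average too small for the stated null, and no other planned output supplies a correct interval for the Week 36/48 average.

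The size rests on an undocumented correlation. Under the assumed inputs the effect is negligible near -0.2. Near -0.3, type I error is about 5.4% to 6.4%. Near -0.55 it is about 8% to 10%, and only if response also depends strongly on true baseline glucose. With a chance mix, the reported half-width is short by about 0.3, 0.6 and 2.0 mg/dL at -0.20, -0.32 and -0.55 (12.0 less 11.7, 11.4 and 10.0).

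The documents do not support a claim that the conclusion is at risk if the drug works as planned. The correction concerns the reported precision, and its priority is modest.

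**What to change.** **Preferred, in SAP 8.3.1.2.** State that the LS mean is evaluated at the mean baseline of the FAS, with each subject counted once. State also that its variance is the Kenward-Roger variance plus b² × s²/n, where b is the fitted baseline slope, s² the sample variance of baseline, and n the number of FAS subjects with a baseline value. Keep the Kenward-Roger degrees of freedom, and apply the same rule to the by-visit LS means.

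The baseline covariate, dependent variable and compound-symmetry fallback stay; under that fallback the corrected type I error was 4.8% to 5.0% (chance) and 3.0% to 4.5% (exact) in the four scenarios tabled. Baseline should not simply be dropped. When simulated dropout depended on baseline, a t-test on subjects with Week 36 or 48 data was biased by +0.5 to +1.6 mg/dL, against at most 0.16 for the LS mean.

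**Alternative.** Model glucose at baseline and at Weeks 24, 36 and 48 jointly as responses, and test the mean of Weeks 36 and 48 minus baseline. List this in SAP 2.1, because Protocol 12.3.3.1 names change as the dependent variable. Compound symmetry does not suit this model, since baseline averages two OGTTs and each follow-up is one; if it does not converge, use the preferred fix.

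**Cost.** Two or three sentences and a few lines of code for the preferred fix, or one paragraph for the alternative; no new data. With a chance mix the CI widens by about 3% at ρ = -0.20 (12.0/11.7), 5% at -0.32 (12.0/11.4) and 20% at -0.55 (12.0/10.0). The test is conservative, at about 3% to 5%, if the mix is held exactly at 1:1.
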